#### 1.1 Design and Treatment

Subjects will receive the administration of Tc 99m tilmanocept through an IV route of administration. All subjects will receive a 150 µg mass dose of tilmanocept labeled with 10 mCi of Tc 99m in a 3 ml volume. Following injection a 10 ml sterile normal saline flush will be administered. The preferred site of IV placement will be the left or right antecubital vein.

Tabl	le 1	Study	arms
------	------	-------	------

Table 1 Study	y arms	
Arm	Subjects	Evaluations
1	HC subjects clinically free of any inflammatory disease and/or joint pain.	Planar image of bilateral hands/wrists.
2	HC subjects clinically free of any inflammatory disease and/or joint pain.  Subjects with clinically diagnosed RA who have been on stable anti-rheumatic therapy.	Planar image of bilateral hands/wrists followed by SPECT/CT of bilateral hands/wrists.

### 1.2 Study Procedures

Subjects will visit the study site (Visit 1) for screening procedures up to 30 days (Day -30 to Day -1) before enrollment into the study. Screening procedures (demographics, vital signs, medical history, blood and urine samples for clinical labs, RA specific labs, urine pregnancy testing for subjects of childbearing potential, and physical exam) will be completed along with the 2010 ACR/EULAR score. RA subjects will also undergo a DAS28 evaluation and a review of RA history including previous treatments, date of symptom onset, and date of diagnosis.

Subjects arriving for Study Day 0 (Visit 2) will be considered enrolled in the study. On Day 0 subjects will receive Tc 99m injection and imaging procedures. A urine pregnancy test will be administered (pre-injection) to all subjects with childbearing potential. Up to 30 minutes prior to drug administration assessment of vital signs and AEs will be performed. After pre-injection procedures are completed subjects will receive a single IV dose with 150  $\mu g$  of tilmanocept radiolabeled with 10 mCi of Tc 99m. Within 30 minutes of injection, subjects will receive vital sign and AE check. For all subjects, planar images of the bilateral hands and wrists will be taken at 60 - 75 minutes for 10 – 13 minutes. After preparation up to 10 minutes, for Arm 2, SPECT/CT of the bilateral hands and wrists will be acquired for 25-30 minutes.

On Study Day 5 ( $\pm$  3 days) (Visit 3) a safety follow-up telephone call will include a review of concomitant medications and assessment of adverse events. Subjects have completed the study at this point.

For all subjects, delegated trained imaging scientists blinded to all clinical subject information will perform semi-automated region-of-interest ROI drawing on planar images of the bilateral hands and wrists to derive relevant count statistics, which are input parameters for TUVjoint and TUVglobal.

#### 1.3 Sample Size

The study will enroll up to 135 evaluable subjects in Arms 1 and 2 allocated below, imaged at up to 8 study centers.

Arm 1 will have up to N = 120 evaluable HC subjects, Arm 2 will have up to N = 15 evaluable subjects; 5 HCs and 10 RA subjects.

A subject is considered evaluable if he/she meets the criteria for the analysis population and has the data necessary for computing the primary endpoint(s) relevant to his/her study Arm.

The sample will be stratified 3:1, females to males ratio to reflect RA incidence in the United States. The sex-specific samples will be further stratified by age to reflect the Census estimated US population in 2019.

The target sample sizes are given below.

Age Range	Male	Female	Total
30 to 39 years	8	23	31
40 to 49 years	7	21	28
50 to 59 years	8	22	30
60 to 69 years	7	21	28
70 years and older	6	21	27
Total	36	108	144

An effort will be made to target enrollment in this group to include 2 men and 8 women 80 years old and over.

The existing data for HC subjects was used in a bootstrap procedure to evaluate the width of 95% confidence intervals for the 95 percentiles for various sample sizes. The sponsor has decided for its business purposes that knowing the percentile to within 0.05 of its true value is sufficient. A sample of size N = 144 HC results (this includes the subjects from Arm 1 of NAV3-31) in 95% confidence intervals with half-widths less than 0.05.

The sample size for Arm 2 was determined to be sufficient for the business purposes of the sponsor. The sample size for Arm 2 will be 5 HCs and 10 RA subjects.

# 2.0 Data Analysis Considerations

#### 2.1 Types of Analyses

Data analyses described in this SAP will consist of analyzing efficacy and safety data.

#### 2.2 Analysis Populations

The following analysis populations will be used in the study:

**Safety Population** – The safety population includes all patients that have been enrolled in the study and injected with Tc 99m tilmanocept.

**Intent-to-Diagnose (ITD) Population** – The ITD population includes all subjects that have been enrolled in the study, injected with Tc 99m tilmanocept, and

received all imaging and evaluations necessary for the primary endpoint(s) appropriate to their respective arm.

**Per Protocol (PP) Population:** The PP population will include all ITD subjects without major protocol violations. All protocol violations will be classified as major or minor prior to database lock.

All efficacy analyses will be carried out on the ITD and PP populations with the ITD population being the primary analysis set. All analyses of safety data and baseline subject characteristics will be carried out on the safety population. A data listing displaying the patients excluded from each population will be created, as shown in Appendix B.

#### 2.3 Missing Data Conventions

No missing value imputation will be used in this analysis. All analyses will be based on the observed data.

#### 2.4 Interim Analyses

There are no interim analyses planned for this study.

#### 2.5 Calculation of TUV

All calculations are done on a reader-specific basis. That is, there is no statistical aggregation of the reader results.

#### Calculating Joint TUV

For an individual joint,  $TUV_{joint}$  is defined as the average pixel intensity of the joint (ROI) divided by the average pixel intensity of the whole hand and part of the forearm on the same view and side as the joint ROI.

#### **Calculating Global TUV**

For each independent blind reader, determine the average  $TUV_{joint}$  and 95% prediction interval of both the anterior and posterior views of the wrists, MCPs, and PIPs in healthy individuals. For all following calculations, reader specific average  $TUV_{joint}$  and 95% prediction intervals will be used.

For each RA subject do the following.

Step 1: Calculate TUVjoint for each of the 22 DAS28 joints for which data are collected.

Step 2: Identify all imaged joints with  $TUV_{joint}$  > upper limit of normal for the anatomically similar joint and view. These will be referred to as inflamed joints (IJ). Each joint has an anterior and posterior view: a joint is considered an IJ if either view has a  $TUV_{joint}$  higher than the upper bound from the normative data set.

Step 3: Calculate the macrophage-involved contribution (MI) to Tc 99m tilmanocept localization for each IJ. This is done by expressing the TUV for the IJ as a fractional change from the mean TUV for the anatomically equivalent joint and view. That is, if  $TUV_{joint}$  and  $\overline{H}_{joint}$  represent the joint and view specific TUV and the mean TUV for the anatomically equivalent joint and view from the normative data set respectively, the macrophage contribution to TUV is  $Ml_{joint}$ :

$$MI_{joint} = \frac{TUV_{joint} - \overline{H}_{joint}}{\overline{H}_{joint}}.$$

Step 4:  $TUV_{global}$  is the total of the macrophage-involved contributions for the IJs. (Note that  $MI_k$  is effectively 0 if  $TUV_{joint}$  is less than or equal to the upper limit of normal from the normative data set.) That is,

$$TUV_{global} = \sum_{All IIs} MI_{IJ} = \sum_{k=1}^{22} MI_k.$$

Arms 1 and 2:

Precision endpoints for both arms will be assessed estimating the mean, standard deviation, n, minimum, median, and maximum of TUV for each evaluated DAS28 joint.

#### 2.6 Study Center Considerations in the Data Analysis

A study center is defined as a treatment administration site or group of treatment administration sites under the control and supervision of the same Principal Investigator (PI). There will be no selective pooling of study centers.

#### 2.7 Documentation and Other Considerations

The data analyses described in this SAP will be conducted using SAS© Software, version 9.4 or later.

# 3.0 Analysis of Baseline Patient Characteristics

Baseline and demographic characteristics of the safety population will be summarized by subject arm and overall. Continuous variables (age, height, and weight) will be summarized via mean, standard deviation, minimum, maximum, and number of non-missing responses. Categorical variables (gender, race, and ethnicity) will be summarized via counts and percentages.

A detailed listing of baseline data for each patient in the safety population will also be provided, as shown in Appendix B.

# 4.0 Analysis of Efficacy

### 4.1 Description of Efficacy Endpoints

The efficacy variables for this study are as follows:

- Quantitative determination of TUVjoint and TUVglobal.
- Qualitative determination of tilmanocept localization in planar images and SPECT/CT images of the bilateral hands and wrists.
- Quantitative determination of tilmanocept localization in planar and SPECT/ CT images of the bilateral hands and wrists

The presence of radiotracer uptake for a joint indicates the presumed presence of activated macrophages. The use of the term "localization" in this SAP is synonymous with the presence of radiotracer uptake.

TUV is defined as:

$$TUV_{joint} = \frac{\bar{X}_{joint}}{\bar{X}_{RR}};$$

where

- $\bar{X}_{joint}$  is the average voxel intensity of a particular joint of a subject at the anterior or posterior views at 1 hour post-injection.
- $\bar{X}_{RR}$  is the average voxel intensity of the reference region (RR) of a subject at the anterior or posterior views at 1 hour post-injection.

# 4.1.1 Primary Efficacy Endpoints

The primary efficacy endpoints of this study are:

#### Arm 1:

The normal limits of TUVjoint per joint basis in HC subjects, which are defined as the 5 and 95 percentiles of TUVjoint of bilateral joints (i.e., bilateral wrists, metacarpophalangeal joint [MCPs], proximal interphalangeal [PIPs]). The normal range will be determined separately for each of the three blinded readers.

#### Arm 2:

The qualitative evaluations of planar and SPECT/CT in detecting localization within synovial spaces of the bilateral hands and wrists in HCs and RA subjects.

### 4.1.2 Secondary efficacy Endpoints

The Secondary efficacy endpoints of this study are:

Healthy Controls in Both Arms 1 and 2:

- Applicability of the Normal (Gaussian) distribution to TUVjoint data.
- Relationship between TUVjoint and age by joint.
- Relationship between the variance of TUVjoint and age.
- Relationship between TUVjoint and sex (male vs female).
- Relationship between TUVjoint and BMI.

#### Arm 2:

- Quantitative evaluations of Tc 99m tilmanocept localization from SPECT/CT within synovial spaces of the bilateral hands and wrists in HCs and RA subjects.
- Normative joint-specific standardized uptake value (SUV).
- Predictive value of planar scans for SPECT/CT scans.

#### 4.2 Analysis of Efficacy Variables

#### 4.2.1 Analysis of Primary Efficacy Variables

#### Arm 1:

All TUVjoint data will be analyzed with summary statistics (mean, standard deviation, n, minimum, median, maximum) by reader, joint and view.

The 5 and 95 percentiles will be estimated with quantile regression fitting an intercept as a fixed term. The lower and upper limits of normal TUVjoint will be determined using non-parametric confidence intervals and kernel density-based confidence intervals.

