### 4.2.2 Analysis of Secondary Efficacy Variables

Healthy Controls in Both Arms 1 and 2:

Normal quantile plots will be provided per-joint and reader, along with the p-value for the Shapiro-Wilk test of Normality.

Scatter plots of  $TUV_{joint}$  by age per-joint will be provided, along with the correlation coefficients and p-values. The hypotheses for the p-value to test the correlation coefficient are:  $H_0$ :  $\rho = 0$  vs  $H_1$ :  $\rho \neq 0$ , where  $\rho$  is the correlation coefficient. The p-value evaluating age in the regression model will be provided in the figure.

Scatter plots of  $TUV_{joint}$  by BMI will be provided, along with the correlation coefficients and p-values. The hypotheses for the p-value to test the correlation coefficient are:  $H_0$ :  $\rho = 0$  vs  $H_1$ :  $\rho \neq 0$ , where  $\rho$  is the correlation coefficient. The p-value evaluating BMI in the regression model will be provided in the figure.

Scatter plots of TUVjoint by sex will be provided.

To check the relationship between the variance of TUVjoint and age, a quantile regression model will be fitted with an intercept as a fixed term. The plot of the residuals on the y-axis and age on the x-axis will be provided.

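### The normal limits ignore sex and age, the declared sex endpoint yields only a plot, and no output shows how many healthy controls of each sex or age band exceed the pooled limit

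*SAP*

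**What the plan says.** Protocol 9.5.3.1 and SAP 4.2.1 (Arm 1) give the same model for the limits: "The 5 and 95 percentiles will be estimated with quantile regression fitting an intercept as a fixed term". The accompanying descriptive statistics are broken down by reader, joint and view, not by sex or age.

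Recruitment is controlled on both factors. SAP 1.3 says: "The sample will be stratified 3:1, females to males ratio to reflect RA incidence in the United States". It continues: "The sex-specific samples will be further stratified by age to reflect the Census estimated US population in 2019". The target is 36 men and 108 women, 144 in all, including controls from NAV3-31.

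SAP 4.1.2 lists as secondary endpoints in healthy controls the relationships of TUV_joint with age, sex and BMI, and of its variance with age. SAP 4.2.2 sets out the analyses:

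- Age: per-joint scatter plots with a correlation coefficient and its p-value, and a p-value for age from a regression model not otherwise specified.
- Variance and age: residuals from an intercept-only quantile regression plotted against age, with no test and no statement of which quantile is fitted.
- BMI: the same treatment as the age correlation.
- Sex: scatter plots "by sex will be provided", and nothing further. Table 11 covers age and BMI only.

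Protocol 9.5.3.4 then uses the 95th percentile for the same reader and joint to call a planar result positive.

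**The concern.** The 95th percentile is the number that will be used. It classifies joints in Arm 2, and Protocol 3.1.1.3 intends the upper limit as reference data for people who present with symptoms. Each such person has a particular sex and age. An intercept-only percentile fixes the exceedance rate at 5% for the recruited mixture, not for any group within it.

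The SAP regards sex and age as possible sources of variation, since it stratifies on both and lists both as endpoints. Yet no planned analysis estimates whether the 95th percentile itself moves with either. At stake is whether the study can report that its limit works about equally well in men and women and across ages, or can say by how much it does not.

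**Working it through.** **The plan's own figures.** The stratum table adds up: men 8+7+8+7+6 = 36, women 23+21+22+21+21 = 108, ratio 3.00. The precision claim at N = 144, "in 95% confidence intervals with half-widths less than 0.05", cannot be reproduced, because neither the bootstrap data nor the SD of TUV_joint is given. As a guide, the shortest exact order-statistic interval for the 95th percentile at n = 144 runs from observation 131 to 142 (coverage 96.3%). Its mean half-width is 0.39 SD for Normal data, so a half-width below 0.05 needs an SD below about 0.05/0.39 = 0.13.

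**Sex.** Assume Normal data with SD 1 in each sex and men shifted by d. The pooled limit q solves 0.75·P(Z > q) + 0.25·P(Z > q − d) = 0.05.

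| d (SD) | q | women flagged | men flagged |
|---|---|---|---|
| +0.25 | 1.72 | 4.3% | 7.1% |
| +0.5 | 1.81 | 3.5% | 9.5% |
| +1.0 | 2.07 | 1.9% | 14.2% |
| −0.5 | 1.55 | 6.0% | 2.0% |

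Check for d = 0.5: 0.75 × 3.5% + 0.25 × 9.5% = 5.0%. With equal means but a male SD 1.25 times the female SD, the rates are 4.0% and 8.0%.

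**Age.** Use the five bands weighted 31/28/30/28/27 and assume a linear trend in the mean. Power is for the planned correlation test (Fisher z) at n = 125, which is the 120 Arm 1 and 5 Arm 2 controls covered by SAP Table 9.

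| slope per decade (SD) | correlation | youngest band flagged | oldest band flagged | power |
|---|---|---|---|---|
| 0.1 | 0.14 | 3.2% | 7.3% | 34% |
| 0.2 | 0.27 | 1.8% | 9.7% | 87% |
| 0.3 | 0.39 | 0.9% | 12.1% | about 100% |

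A correlation addresses the mean. Suppose instead that the mean is flat and the SD rises per decade by 10% of its youngest-band value. The true correlation is then zero, yet the pooled limit flags 2.4% of the youngest band and 7.9% of the oldest. Only the residual plot could show that.

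**Precision of a sex term at the 95th percentile.** For Normal data the asymptotic SE is √(0.95 × 0.05)/φ(1.645) × √(1/n_men + 1/n_women) = 2.113 × √(1/36 + 1/108) = 0.41 SD. The 95% half-width is 1.96 × 0.41 = 0.80 SD. Table 9 would contain about 31 men and 94 women (3:1 of 125), which gives 0.86 SD.

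**Separate limits for men.** With n = 36 the sample maximum exceeds the true 95th percentile with probability 1 − 0.95^36 = 0.842. A two-sided 95% order-statistic interval needs 0.95^n ≤ 0.025, so n ≥ 72.

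**The case against.** A reader might infer that unequal rates by age would go undetected. The documents do not support that. SAP 4.2.2 tests age per joint and plots residuals against age. A trend of 0.2 SD per decade, enough to move the flagged share from 1.8% to 9.7%, would be found with about 87% power. What remains for age is narrower: the test addresses the mean rather than the percentile, the residual plot carries no test, and small trends have low power.

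A reader might also infer that the pooled limit does give unequal rates. Nothing in the documents shows this. TUV_joint is a ratio to a reference region on the same hand and view, which may remove part of any difference between people. The shifts used above are assumptions.

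Nor is pooling an error. The mix was chosen deliberately (the 3:1 ratio reflects RA incidence), and a marginal limit for that mix is a legitimate reference.

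For sex, a large difference would be visible in a plot. The Figure 7 shell note in SAP Appendix B says its format repeats for sex, and the figure itself is not available here, so it might carry more than a plot. The SAP text, however, promises no estimate, and Table 11 has no row for sex. That part of the concern stands.

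**Conclusion.** The point holds in a limited form. The limits ignore the two factors on which the sample is stratified. The declared sex endpoint produces no number, age is tested only as a trend in the mean, and exceedance of the pooled limit is not reported by sex or age band.

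If the 95th percentile varies with sex, the gap could be modest (4.3% of women against 7.1% of men at 0.25 SD) or large (1.9% against 14.2% at 1 SD). These figures assume Normal data and shifts for which the documents give no anchor. They show what the plan could fail to quantify, not what it will find. The primary analysis does not need to change, but a supportive one should be added.

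**What to change.** Keep the pooled limits as primary. Add to SAP 4.2.2, for healthy controls:

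1. A supportive quantile regression at the 5th and 95th percentiles with age (continuous, per decade) and sex as fixed effects, by reader, joint and view, reporting the coefficients with bootstrap confidence intervals.
2. The percentage of healthy controls above the pooled limit, by sex and by age band.

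Do not compute separate nonparametric limits for men, because 36 are too few.

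Do not use the 0.05 in SAP 1.3 as a trigger for sex-specific limits. It is a precision target for a percentile, not a tolerance for a difference between groups. With no true effect and 36/108 subjects, a simulation gave a sex-coefficient SE of about 0.43 SD, close to the 0.41 above. The estimate exceeded 0.05 by chance in about 36% of fits at an assumed SD of 0.13, and in 23% at 0.10. There would be 66 such fits (11 joint types × 2 views × 3 readers), or 132 if left and right are kept apart.

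The cost is a little more analysis on data already collected. The sex estimates will be imprecise (95% half-width about 0.8 SD, wider with about 31 men), so the results must be labelled supportive.

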#### Arm 2.

Localization of tilmanocept in the hands and wrists will be summarized with frequency counts and percentages by reader and joint.

### 4.2.2 Analysis of Secondary Efficacy Variables

Healthy Controls in Both Arms 1 and 2:

Normal quantile plots will be provided per-joint and reader, along with the p-value for the Shapiro-Wilk test of Normality.

Scatter plots of  $TUV_{joint}$  by age per-joint will be provided, along with the correlation coefficients and p-values. The hypotheses for the p-value to test the correlation coefficient are:  $H_0$ :  $\rho = 0$  vs  $H_1$ :  $\rho \neq 0$ , where  $\rho$  is the correlation coefficient. The p-value evaluating age in the regression model will be provided in the figure.

Scatter plots of  $TUV_{joint}$  by BMI will be provided, along with the correlation coefficients and p-values. The hypotheses for the p-value to test the correlation coefficient are:  $H_0$ :  $\rho = 0$  vs  $H_1$ :  $\rho \neq 0$ , where  $\rho$  is the correlation coefficient. The p-value evaluating BMI in the regression model will be provided in the figure.

Scatter plots of TUVjoint by sex will be provided.

To check the relationship between the variance of TUVjoint and age, a quantile regression model will be fitted with an intercept as a fixed term. The plot of the residuals on the y-axis and age on the x-axis will be provided.

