Table No.	Table Title	Included in Final Tables	Shown in Appendix B
25	Serum Chemistry Clinical Laboratory Parameters Summary Statistics by Arm (Safety Population)	X	X
26	Hematology Clinical Laboratory Parameters Summary Statistics by Arm (Safety Population)	X	
27	Urinalysis Clinical Laboratory Parameters Summary Statistics by Arm (Safety Population)	X	
28	Serum Chemistry Clinical Laboratory Parameters Shift Table by Arm (Safety Population)	Х	Х
29	Hematology Clinical Laboratory Parameters Shift Table by Arm (Safety Population)	Х	
30	Urinalysis Clinical Laboratory Parameters Shift Table by Arm (Safety Population)	Х	
31	Vital Signs Summary Statistics by Arm (Safety Population)	Χ	Х

Figure No.	Figure Title	Included in Final Figures	Shown in Appendix B
Fig1	Normal QQ plot for TUV joint Data – All Arm 1 and 2 Healthy Control Subjects (ITD Population)	Х	X
Fig2	Normal QQ plot for TUV joint Data – All Arm 1 and 2 Healthy Control Subjects (PP Population)	Х	
Fig3	Scatter Plot of TUV joint Distribution of the Right Hand – All Arm 1 and 2 Healthy Control Subjects (ITD Population)	Х	Х
Fig4	Scatter Plot of TUV joint Distribution of the Right Hand – All Arm 1 and 2 Healthy Control Subjects (PP Population)	Х	
Fig5	Scatter Plot of TUV joint Distribution of the Left Hand – All Arm 1 and 2 Healthy Control Subjects (ITD Population)	Х	Х
Fig6	Scatter Plot of TUV joint Distribution of the Left Hand – All Arm 1 and 2 Healthy Control Subjects (PP Population)	Х	
Fig7	Scatter Plot of TUV joint Distribution for MCP1 by Age – All Arm 1 and 2 Healthy Control Subjects (ITD Population)	Х	Х
Fig8	Scatter Plot of TUV joint Distribution for MCP1 by Age – All Arm 1 and 2 Healthy Control Subjects (PP Population)	Х	
Fig9	Scatter Plot of TUV joint Distribution for MCP2 by Age – All Arm 1 and 2 Healthy Control Subjects (ITD Population)	Х	
Fig10	Scatter Plot of TUV joint Distribution for MCP2 by Age – All Arm 1 and 2 Healthy Control Subjects (PP Population)	Х	
Fig11	Scatter Plot of TUV joint Distribution for MCP3 by Age – All Arm 1 and 2 Healthy Control Subjects (ITD Population)	Х	
Fig12	Scatter Plot of TUV joint Distribution for MCP3 by Age – All Arm 1 and 2 Healthy Control Subjects (PP Population)	Х	
Fig13	Scatter Plot of TUV joint Distribution for MCP4 by Age – All Arm 1 and 2 Healthy Control Subjects (ITD Population)	Х	

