Fig14	Scatter Plot of TUV joint Distribution for MCP4 by Age – All Arm 1 and 2 Healthy Control Subjects (PP Population)	Х	
Fig15	Scatter Plot of TUV joint Distribution for MCP5 by Age – All Arm 1 and 2 Healthy Control Subjects (ITD Population)	Х	

Figure		Included in Final	Shown in Appendix
No.	Figure Title	Figures	В
Fig16	Scatter Plot of TUV joint Distribution for MCP5 by Age – All Arm 1	Х	
	and 2 Healthy Control Subjects (PP Population)		
Fig17	Scatter Plot of TUV joint Distribution for PIP1 by Age – All Arm 1	X	
	and 2 Healthy Control Subjects (ITD Population)		
Fig18	Scatter Plot of TUV joint Distribution for PIP1 by Age – All Arm 1	X	
	and 2 Healthy Control Subjects (PP Population)		
Fig19	Scatter Plot of TUV joint Distribution for PIP2 by Age – All Arm 1	Х	
	and 2 Healthy Control Subjects (ITD Population)		
Fig20	Scatter Plot of TUV joint Distribution for PIP2 by Age – All Arm 1	X	
	and 2 Healthy Control Subjects (PP Population)		
Fig21	Scatter Plot of TUV joint Distribution for PIP3 by Age – All Arm 1	X	
	and 2 Healthy Control Subjects (ITD Population)		
Fig22	Scatter Plot of TUV joint Distribution for PIP3 by Age – All Arm 1	X	
	and 2 Healthy Control Subjects (PP Population)		
Fig23	Scatter Plot of TUV joint Distribution for PIP4 by Age – All Arm 1	X	
	and 2 Healthy Control Subjects (ITD Population)		
Fig24	Scatter Plot of TUV joint Distribution for PIP4 by Age – All Arm 1	X	
	and 2 Healthy Control Subjects (PP Population)		
Fig25	Scatter Plot of TUV joint Distribution for PIP5 by Age – All Arm 1	X	
	and 2 Healthy Control Subjects (ITD Population)		
Fig26	Scatter Plot of TUV joint Distribution for PIP5 by Age – All Arm 1	X	
	and 2 Healthy Control Subjects (PP Population)		
Fig27	Scatter Plot of TUV joint Distribution for Wrist by Age – All Arm 1	Х	
	and 2 Healthy Control Subjects (ITD Population)		
Fig28	Scatter Plot of TUV joint Distribution for Wrist by Age – All Arm 1	Х	
	and 2 Healthy Control Subjects (PP Population)		
Fig29	Scatter Plot of TUV joint Distribution by Sex – All Arm 1 and 2	X	
	Healthy Control Subjects (ITD Population)		
Fig30	Scatter Plot of TUV joint Distribution by Sex – All Arm 1 and 2	X	
	Healthy Control Subjects (PP Population)		
Fig31	Scatter Plot of TUV joint Distribution by BMI – All Arm 1 and 2	X	

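### The age and BMI p-values make no allowance for repeated TUVjoint values per control; if rows are pooled, as the layouts imply, they are miscalibrated

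*SAP*

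**What the plan says.** SAP 4.2.2, under "Healthy Controls in Both Arms 1 and 2", plans scatter plots of TUVjoint by age for each joint, and by BMI, "along with the correlation coefficients and p-values". The test is two-sided, of zero against non-zero correlation. A regression p-value is added for each covariate: "The p-value evaluating age in the regression model will be provided in the figure" and "The p-value evaluating BMI in the regression model will be provided in the figure". The regression model itself is not written out.

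SAP 1.0 gives 22 DAS28 joints per subject in the hands and wrists. SAP 2.5 adds: "Each joint has an anterior and posterior view". The same section keeps the three readers separate. SAP 2.3 says only that analyses use observed data without imputation.

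The outputs are laid out as follows.

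- The age figures (SAP 7.0, Figures 7–28) have titles such as "Distribution for MCP1 by Age – All Arm 1 and 2 Healthy Control Subjects (ITD Population". They cover MCP1–5, PIP1–5 and wrist, which is 11 joint types rather than 22 joints, and no title names a side or view.
- The BMI figures (31 and 32) are titled "Distribution by BMI – All Arm 1 and 2", one per analysis population. A note under the Figure 7 shell in Appendix B, however, extends the per-joint format to sex and BMI.
- The Table 11 shell has a single age row and a single BMI row, with no joint, side, view or reader column.

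**The concern.** A control's age and BMI are the same on every one of that control's rows. The standard test of a correlation or slope assumes independent rows. If a control's TUVjoint values resemble each other across sides, views or joints, extra rows add less information about age or BMI than the test credits, and the p-value comes out too small.

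The SAP lists the relationships with age and BMI as secondary endpoints (4.1.2). They bear on whether one normal range can serve all ages and body sizes, in a study that recruits by age band to build a normative database. A spuriously small p-value could be read as a case for age- or BMI-specific limits that the data do not support.

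**Working it through.** The documents give no alpha, power or sample size for these tests, so there is no planned figure to reproduce.

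**Inputs from the documents**

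- Controls: 120 in Arm 1 + 5 in Arm 2 = 125 (SAP 1.3). A variant of 144 includes the earlier study's controls.
- Rows per control, per reader (k): 2 if only the sides of a joint type are pooled; 2 sides × 2 views = 4 if an age figure holds everything its title covers; 22 joints × 2 views = 44 if Table 11 is run as drawn.

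**Assumptions**

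- Nominal two-sided 5% level.
- Pearson correlation and simple linear regression. With one covariate the slope and correlation tests give the same p-value.
- Within-subject correlation (ICC) of 0.2, 0.5 or 0.8. The documents give no value.
- Exchangeable rows at first, that is, no mean differences between views or joints.

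**Step 1: exchangeable rows.** For a covariate that is constant within subject, the variance is understated by 1 + (k − 1) × ICC, so the actual rate of p < 0.05 under no relationship is

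2 × [1 − Φ(1.96 / √(1 + (k − 1) × ICC))].

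Example with k = 4 and ICC = 0.5: 1 + 3 × 0.5 = 2.5; 1.96 / √2.5 = 1.24; rate = 21.5%.

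| Rows per control | ICC 0.2 | ICC 0.5 | ICC 0.8 |
|---|---|---|---|
| 2 (sides) | 7.4% | 11.0% | 14.4% |
| 4 (sides × views) | 12.1% | 21.5% | 28.8% |
| 44 (all joints × views) | 52.7% | 67.9% | 74.2% |

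Simulation with 125 controls (4,000 runs per cell) agrees: 12.1%, 20.8% and 30.1% for 4 rows, and 53.0%, 67.8% and 74.7% for 44. Results at 144 controls are much the same, so a larger sample does not cure the problem. At ICC = 0 the rate is 5%.

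**Step 2: fixed differences between views or joints.** If such differences, common to all controls and left out of the model, take a share f of the total variance, they inflate the residual variance. The factor becomes (1 − f) × (1 + (k − 1) × ICC), with ICC referring to the remaining variance. At ICC 0.5:

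| Rows per control | f = 0 | f = 0.25 | f = 0.5 | f = 0.75 | f = 0.9 |
|---|---|---|---|---|---|
| 4 | 21.5% | 15.2% | 8.0% | 1.3% | <0.1% |
| 44 | 67.9% | 63.3% | 55.9% | 40.9% | 19.1% |

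At ICC 0.2 and f = 0.9 the 44-row rate is 4.5%. The pooled test can therefore err in either direction.

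**Step 3: one value per control.** Averaging to one value per control before testing gave simulated rates of 4.6% to 5.4% for k = 2, 4 and 44 and ICC 0 to 0.8, at 125 and at 144 controls. That is nominal within simulation error.

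**The case against.** The strongest reply is that pooling is inferred. No sentence in the SAP says that sides and views count as independent observations, and a reader who takes that from the layouts as a stated rule goes further than the text does. The plots are not visible, so separate panels cannot be excluded. Elsewhere the plan does separate these levels: the TUVjoint summaries are by reader, joint and view, Tables 5 and 9 have a view column, and Figures 3–6 split right from left hand. A single-row shell is also weak evidence. Table 15 has one row for Shapiro-Wilk although the text asks for that test by joint and reader. All of this stands, and it is why the conclusion is conditional. It does not supply the missing unit of analysis, and the contrast with Figures 3–6 shows that the SAP names the side in a title when it means to split by it.

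On BMI, a reader of the figure list might infer that 44 rows per control go into one plot. The shell note points to BMI figures per joint, so the two places disagree and the 44-row case cannot be rested on Figures 31 and 32. It rests on Table 11 as drawn.

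On size, the ICC is unknown. Each TUVjoint is divided by a reference from its own view and side, so high correlation across all rows cannot be presumed. Exchangeability is least credible when wrist, MCP and PIP values are mixed. Both points stand; Step 2 shows their effect.

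On consequences, a reader might infer that these p-values decide whether limits are split by age or BMI. The SAP sets no alpha and no such rule, and the normal limits come from an intercept-only quantile regression that these tests do not alter. Nor are all four listed relationships tested: sex gets plots only, and variance against age gets a residual plot.

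**Conclusion.** The point holds in conditional form. SAP 4.2.2 plans ordinary p-values for two subject-level covariates without accounting for repeated values per subject, and its layouts imply several rows per control. If rows are pooled, the p-values are miscalibrated. With exchangeable rows, a 5% benchmark and ICC 0.2–0.8, false positives run at about 7–14% (sides), 12–29% (sides and views) or 53–74% (all 44 values). The level, the ICC and exchangeability are assumptions. Large fixed differences between views or joints reduce the rates, and in the 4-row case can take them well below 5%.

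The effect is confined to the age and BMI secondary endpoints. It should be corrected before the analysis is programmed, but it does not threaten the primary result.

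**What to change.** State in SAP 4.2.2 that the unit of analysis is the subject. Either of two methods will do:

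- For each reader, joint type and view, average left and right to one value per control, then compute the correlation, slope and p-value.
- Keep all rows and use subject-clustered standard errors or a subject random effect, with terms for side and view.

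Give Table 11 rows by joint, view and reader; with sides averaged that is 11 × 2 × 3 = 66 rows per covariate. Reconcile the listing of Figures 31 and 32 with the shell note that extends the per-joint format to BMI. Print the number of subjects beside each p-value.

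The cost is a few sentences in the SAP, a longer Table 11 and a small programming change, with no new data. The p-values will change. They will usually become larger, but could become smaller where fixed differences between views or joints had made the pooled test conservative.
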